3 OBJECTIVES

3.1 Primary objective

To compare the effect of discontinuation versus continuation of RAS blockers on the clinical course of patients with confirmed COVID-19 infection leading to hospitalization

3.2 Secondary objectives

- To evaluate the safety of RAS blockers discontinuation on a composite endpoint of major adverse cardiac events defined as the composite of cardiovascular death, myocardial infarction, stroke or acute heart failure at day 28.
- To evaluate the efficacy of RAS blockers discontinuation:
 1. Clinical status as assessed with the seven-category ordinal scale on day 28.
 2. Number of days alive free of oxygen.

3. Number of days alive outside hospital during 28 days after randomization.
4. Number of days alive free of intensive-care unit (ICU) admission or mechanical ventilation (invasive or non-invasive) 28 days after randomization.
5. Number of days alive free of mechanical ventilation (invasive or non-invasive) 28 days after randomization.
6. Number of days alive free of ICU admission 28 days after randomization.
7. Rate of all-cause mortality at day 28.
8. Rate of cardiovascular death at day 28.
9. Number of days alive free of acute kidney injury during hospitalization.

4 **STUDY DESIGN**

4.1 ***Study endpoints***

4.1.1 **Primary endpoint**

The primary endpoint of the study is the time to clinical improvement from day 0 to day 28, defined as an improvement of two points on a seven-category ordinal scale, or live discharge from the hospital (whichever comes first), as recommended by the WHO R&D Blueprint expert group (3).

The seven-category ordinal scale consisted of the following categories:

1. not hospitalized with resumption of normal activities
2. not hospitalized, but unable to resume normal activities
3. hospitalized, not requiring supplemental oxygen
4. hospitalized, requiring supplemental oxygen
5. hospitalized, requiring nasal high-flow oxygen therapy, noninvasive mechanical ventilation, or both
6. hospitalized, requiring ECMO, invasive mechanical ventilation, or both
7. death.

4.1.2 **Secondary endpoints**

1. **Primary safety endpoint:** major adverse cardiac events defined as the composite of cardiovascular death, myocardial infarction, stroke or acute heart failure at day 28.
2. **Key secondary efficacy endpoints:**
 - Clinical status as assessed with the seven-category ordinal scale on days 28.
 - Number of days alive free of oxygen.
 - Number of days alive outside hospital during 28 days after randomization.
 - Number of days alive free of intensive-care unit (ICU) admission or mechanical ventilation (invasive or non-invasive) 28 days after randomization.
 - Number of days alive free of mechanical ventilation (invasive or non-invasive) 28 days after randomization.
 - Number of days alive free of ICU admission 28 days after randomization.

- Rate of all-cause mortality at day 28.
- Rate of cardiovascular death at day 28.
- Number of days alive free of acute kidney injury during hospitalization.

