5.2 Every day visit in hospitalization until day 28, discharge or death

The patients will have a daily visit during hospitalization until day 28, discharge or death. All the events occurring during hospitalization will be collected prospectively, as well as the date of onset:

- Clinical status on a seven-category ordinary scale (as defined above) each day
- Hospital discharge
- Cross-over
- Cardiovascular death
- Non cardiovascular death and cause
- myocardial infarction
- Myocarditis
- Stroke
- Heart failure; presence of congestive signs, IV use of diuretics
- Acute kidney injury, as defined in the KDIGO (Kidney Disease: Improving Global Outcomes) guidelines (45): increase in serum creatinine $\geq 26.5 \mu\text{mol/L}$ within 48h or ≥ 1.5 times baseline within the last 7 days or urine output $< 0,5 \text{ ml/kg/h}$ for 6 hours
- ICU admission (and date of discharge if happens)
- Oxygen requirement: date of beginning and cessation
- Mechanical ventilation (non-invasive or invasive): date of beginning and cessation
- Acute respiratory distress syndrome, as define by the Berlin criteria (46): acute lung injury ≤ 1 week, bilateral opacities consistent on chest imaging not fully explained by other lung pathology, heart failure or volume overload, $\text{PaO}_2/\text{FiO}_2$ ratio $\leq 300\text{mmHg}$ with a minimum of 5 cm H_2O PEEP (or CPAP)
- Shock requiring vasopressors
- Extracorporeal membrane oxygenation (ECMO): date of beginning and cessation
- Renal replacement therapy: date of beginning and cessation
- Biology: as mentioned at 5.1, according to the physician's decision

5.3 End of study visit (visit or phone call at day 28 \pm 4 days)

- All patients still hospitalized at day 28, will have a visit with an events collection as mentioned at 5.2.
- All survivors' patients already discharged from hospital will have a phone call by an investigator (physician) at day 28 (± 4 days) to collect the events occurred since discharge from hospital:
 - Clinical status on a seven-category ordinary scale (as defined above)
 - New hospitalization in a non-ICU
 - Cardiovascular death

- Non cardiovascular death and cause
- Myocardial infarction
- Myocarditis
- Stroke
- Heart failure; presence of congestive signs, IV use of diuretics
- Acute kidney injury, as defined in the KDIGO guidelines
- ICU admission
- Oxygen requirement: date of beginning and cessation
- Mechanical ventilation (non-invasive or invasive): date of beginning and cessation

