12.4.2 Secondary Efficacy Criteria

If a significant difference is found for the main criterion, The secondary criteria will be tested using a hierarchical procedure in the following order:

1. Clinical status as assessed with the seven-category ordinal scale on days 28.
3. Number of days alive free of oxygen.
4. Number of days alive outside hospital during 28 days after randomization.
5. Number of days alive free of intensive-care unit (ICU) admission or mechanical ventilation (invasive or non-invasive) 28 days after randomization.
6. Number of days alive free of mechanical ventilation (invasive or non-invasive) 28 days after randomization.
7. Number of days alive free of ICU admission 28 days after randomization.
8. Rate of all-cause mortality at day 28.
9. Rate of cardiovascular death at day 28.
10. Number of days alive free of acute kidney injury during hospitalization.

Secondary criteria will be compared using Mann-Whitney tests for quantitative variables and ordinal logistic regression to analyze the seven-category ordinal. Chi-square tests for categorical data and Cox survival analysis for time to event. Tests will be performed at a two-sided 5% significant level for one criterion only if a significant difference has been found for the previous criterion in the list.

Differences in medians between groups will be reported with associated 95% CI

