12.8 Sample size issues

This trial is designed in a public health emergency context, at which time there is limited information about clinical outcomes in Covid-19 hospitalized patients.

We will include $n=277$ patients in each group to provide the trial with 90% power to detect a difference, at a two-sided global significance level of $\alpha = 0.05$, of 5 days in the median time to clinical improvement between the two groups, assuming that the median time in the standard-care group will be 16 days (B. Cao et al NEJM March 18th 2020). We considered 3 equally spaced analyses allowing early stopping for efficacy according to the O'Brien-Fleming boundaries.

Considering around 25 % of patients in the cardiac insufficiency stratum, we also checked that, in case of significant interaction between stratum and treatment due to a minor effect of the treatment in patients with cardiac insufficiency, this sample size will also allow 80% to detect a 5 days in the median time to clinical improvement in the other stratum that will include $n=207$ patients/group.

Primary efficacy analysis will be on an intention-to-treat basis and included all the patients who had undergone randomization.

The time to clinical improvement will be assessed after day 28, and absence of clinical improvement or death before day 28 will be considered as right-censored at day 28.

The time to clinical improvement will be analyzed by Kaplan-Meier method and compared with a log-rank test.

In addition a blinded sample size reassessment procedure will be performed at the second interim analysis that would allow the data safety monitoring board to recommend, if required, an increase of the sample size to reach the expected power.

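### AKI-free days are counted over the hospital stay, so the arm discharged sooner scores worse even with equal or less AKI

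*Protocol*

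**What the plan says.** The Summary and sections 3.2, 4.1.2 and 12.4.2 all give the renal endpoint as "Number of days alive free of acute kidney injury during hospitalization". None of them adds a fixed window.

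There are six day-count endpoints. Four state 28 days after randomisation: "Number of days alive outside hospital during 28 days after randomization", and the three counts for ICU admission, mechanical ventilation and the two combined. The oxygen count, "Number of days alive free of oxygen", states no window but is not tied to the stay. Only the AKI count is.

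Section 12.4.2 sets the analysis: "Secondary criteria will be compared using Mann-Whitney tests for quantitative variables", and "Differences in medians between groups will be reported with associated 95% CI". The criteria are ordered: "Tests will be performed at a two-sided 5% significant level for one criterion only if a significant difference has been found for the previous criterion". AKI-free days are the last of the nine listed criteria.

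On data, section 5.2 records AKI with its date of onset during the stay. Section 5.3 asks about "Acute kidney injury, as defined in the KDIGO guidelines" after discharge. Both sections list start and stop dates for oxygen, ventilation, ECMO and renal replacement, but not for AKI.

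**The concern.** The length of the count is itself an outcome of treatment. Section 2.7 names faster recovery and discharge as an expected benefit of discontinuation, and live discharge is part of the primary endpoint. If discontinuation works as hypothesised, its patients have fewer hospital days on which to be free of AKI, and the count falls for a reason that has nothing to do with the kidney.

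Sections 2.3 and 2.7 give less AKI as part of the rationale. A distorted renal estimate could therefore make a real renal benefit look like renal harm.

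**Working it through.** The protocol gives no planning figure for this endpoint. Its sample size concerns the primary endpoint and is not in dispute here.

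**1. Scoring by hand.** As written, score = days alive in hospital − AKI days. Over a fixed window, score = days alive up to day 28 − AKI days.

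| Patient | As written | Fixed 28 days |
|---|---|---|
| A: discharged well on day 6, no AKI | 6 − 0 = 6 | 28 − 0 = 28 |
| B: in hospital 28 days, 10 days of AKI | 28 − 10 = 18 | 28 − 10 = 18 |
| C: dies on day 6, no AKI | 6 − 0 = 6 | 6 − 0 = 6 |

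As written, B ranks above A, and A ties with C. The fixed window puts them in the sensible order.

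**2. Size of the effect (illustration).**

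Inputs from the protocol:
- 277 per arm; medians 16 and 16 − 5 = 11 days (section 12.8, stated for time to improvement).
- 22% mortality at day 28 (section 10.3.2.2).
- AKI 3–15% (section 2.2, where it is listed among causes of ICU admission).

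Assumptions:
- Stay is exponential with those medians, capped at day 28.
- Deaths occur in hospital, uniformly over days 1–28.
- AKI starts in the first week and lasts about a week (7 days, or 3–10 days).
- Two-sided Mann-Whitney test at 5%.

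| AKI, continuation vs discontinuation | As written: significant against the faster-discharged arm | Fixed 28 days: significant |
|---|---|---|
| Equal, 22% deaths | 79–83% | 4–6%, either direction |
| 15% vs 7.5%, 22% deaths | about 60–70% | 28% for less AKI, 0% against |
| 10% vs 5%, 22% deaths | 74% | 16% |
| 15% vs 0%, 22% deaths | 47% | 80% |
| Equal, no deaths | 94–95% | 4–5% |
| 10% vs 5%, no deaths | 90% | 62% |

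As written, the test never favoured the arm with less AKI. With equal AKI the median scores were 15–16 vs 11–12 days (22% deaths) or 16 vs 11 (no deaths). The gap of roughly 3–5 days comes from stay alone.

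**3. Effect of the hierarchy.** With mortality equal at 22%, the all-cause mortality step is passed in about 5% of trials. A wrong-direction AKI result that also passes that step occurs in about 4% (4.3% with equal AKI, 3.4% with 15% vs 7.5%). If mortality is 22% vs 13%, the figure is 53–68%. Both are before the other gates.

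**4. Difference in medians on the other counts.** The median of a 28-day count stays at 28 while fewer than half of the arm has the event or dies.
- ICU: admission is 5–32% (section 2.2) and mortality 22%. At 32%, the affected share lies between 32% (full overlap) and 32 + 22 = 54% (none); if independent, 1 − 0.68 × 0.78 = 47%. At 5% it is 22–27%.
- Ventilation, with ARDS at 3–42% as the only proxy: at 42%, between 42% and 42 + 22 = 64%; if independent, 1 − 0.58 × 0.78 = 55%. At 3% it is 22–25%.
- Days outside hospital: medians near 28 − 16 = 12 and 28 − 11 = 17, so a difference is visible.
- Oxygen-free days are not shown to be at a ceiling. The AKI count as written is not at one, since it follows the stay.

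So three of the six counts (ICU, ventilation, and the two combined) probably have both medians at 28.

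**The case against.** **The wording may mean only where AKI is ascertained.** Days could be meant to run to day 28, with AKI looked for in hospital. The artefact would then disappear. But the text does not say so, and the explicit 28-day wording on neighbouring endpoints points the other way. This is a reason to fix the wording.

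**The hierarchy protects the trial.** A reader might infer from the 80% figure that a false formal finding of renal harm is likely. The protocol does not support that: the endpoint is tested last, and with equal mortality the mortality step alone cuts such results to about 4%. The protection is incomplete. If the gates open, days outside hospital has already differed, which is when the artefact is active, and the tests are two-sided. The plan to report differences in medians is not made conditional on passing the gates.

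**The stay medians are borrowed.** This stands. The protocol gives no length-of-stay assumption, so the percentages illustrate the problem; they do not predict results. The direction follows from the scoring alone.

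**Medians are only descriptive.** This also stands in part. A reader might infer that the planned analysis cannot show an effect on most day counts. Three of six is not most; at the upper end of the protocol's rates the medians can leave 28; and the Mann-Whitney test still works at a ceiling. Only the reported effect size is uninformative. A further measure could also be set in an analysis plan that is not available here.

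**Conclusion.** On its literal wording, the AKI endpoint penalises earlier discharge and scores it the same as early death. If stay shortens from a median of 16 to 11 days with 22% mortality, the ungated test is significantly against the faster-discharged arm in about 80% of trials with equal AKI and about 60–70% with AKI halved. Formal wrong-direction results are much rarer unless mortality also differs. The estimate is distorted whether or not the gate is reached.

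The median point is secondary: for about three of six counts the reported difference will usually be 0 even when the test detects an effect.

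A reader might also infer, because section 5.3 asks about AKI after discharge, that a 28-day count needs only a change of words. It does not follow. No AKI end date is listed, discharged patients are contacted by phone, and section 5.5 plans day-28 laboratory tests only for those still in hospital, while the AKI definition in section 8.1.6 needs creatinine or urine output.

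The endpoint is secondary and last in order. The primary analysis and sample size are unaffected, but the correction is worth making before data are seen.

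**What to change.** In the Summary and sections 3.2, 4.1.2 and 12.4.2, redefine the endpoint as days alive and free of AKI during the 28 days after randomisation. State three rules:
- Days after death count as not free.
- Days after discharge count as AKI-free unless AKI is reported at the day-28 contact.
- An AKI episode ends on a recorded date, which is added to the CRF.

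Give oxygen-free days the same 28-day window.

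In section 12.4.2, report a mean difference or the Mann-Whitney probability, with 95% CI, beside the difference in medians for the day counts. Recounting AKI over 28 days brings that count to the ceiling as well (median 28 in both arms in the simulations), so it needs the extra measure too.

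The cost is one CRF date and less certain AKI ascertainment after discharge, which should be acknowledged when the result is reported.

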4.2 Description of research methodology

4.2.1 Design of the study

ACORES-2 will be a phase III national, multicenter, comparative, controlled, randomized, open label trial in parallel groups among patients hospitalized for COVID-19 and treated with RAS blockers.

It will test the superiority of the “discontinuation strategy” versus the “continuation strategy”. Participants will be distributed in a 1:1 ratio between the 2 groups.

4.2.2 Number of participating sites

We are expecting to enroll 554 patients (277 in each arm) in 12 French centers.

4.2.3 Identification of participants

The participants in this research will be identified as follows:

Site number. (3 digits) - Sequential enrolment number for the site (4 digits) - surname initial - first name initial

This reference number is unique and will be used for the entire duration of the study.

A randomization number will also be assigned when the participant is randomized. This number will have the following format: RXXX

4.2.4 Randomization

Randomization will be performed with IWRS (Cleanweb).

[figure not shown]
URC Lariboisière Saint-Louis will be done randomization list according to AP-HP Standard Operating Procedures (SOP).

Patients fulfilling the inclusion criteria and without any exclusion criteria that agree to enter the protocol and have signed the inform consent form during the consultation (inclusion) will be randomized in a 1:1 ratio to:

- Group Discontinuation = discontinuation of RAS blocker therapy until the end of the study which correspond to day 28 (experimental arm). After day 28, RAS blockers could be reintroduced or not, according to the physician decision.
or
- Group Continuation = continuation of RAS blocker therapy (control arm)

The randomization will be stratified on the indication of RAS blockers (heart failure vs. other indication).

Inclusion and randomization will be done the same day.

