	
Consecutive patients with a diagnosis of COVID-19 confirmed by the presence of SARS-CoV-2 on any biological sample with any detection method requiring hospitalization will be enrolled.
 
Patients will be randomly assigned in a 1:1 ratio to continue (group continuation) or not (group discontinuation) their usual RAS blockers therapy plus standard of care (oxygen, noninvasive or invasive ventilation, antibiotics, vasopressor support, renal-replacement therapy, circulatory assistance if needed). The randomization will be stratified on the indication of RAS blockers (heart failure vs. other indication).
 
If the patients' usual treatment is not available in the hospital, a switch to ramipril for ACE inhibitors or valsartan for ARBs will be done in the continuation group or in case of cross-over.
 
Written information consent will be obtained from all patients.
 
All the medical data and outcomes will be record prospectively.
 
A phone call will be done at day 28 (\pm 4 days) for all survivor's patients.

Population of study participants	Adult patients with a diagnosis of COVID-19 requiring hospitalization and on prior therapy with RAS blockers.
Inclusion criteria	
Subjects meeting all of the following criteria will be considered for enrolment into the study:
 
 1. Age \geq 18 year/old 2. Chronically treated with RAS blockers (ACE inhibitors or ARBs on the last prescription prior to admission with a treatment duration \geq 1 month) 3. Diagnosis of COVID-19 confirmed by the presence of SARS-CoV-2 on any biological sample with any detection method 4. Patients hospitalized 5. Negative pregnancy test at inclusion visit for women of childbearing potential 6. Women of childbearing potential must agree to use adequate contraception according to Recommendations related to contraception and pregnancy testing in clinical trials, by Clinical Trial Facilitation Group (CTFG)
Exclusion criteria	
Subjects presenting with any of the following will not be included in the study:
 
 1. Shock requiring vasoactive agents

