	
to detect a 5 days in the median time to clinical improvement in the other stratum that will include n=207 patients/group.
 
Primary efficacy analysis will be on an intention-to-treat basis and included all the patients who had undergone randomization.
 
The time to clinical improvement will be assess after day 28, and absence of clinical improvement or death before day 28 will be considered as right-censored at day 28.
 
The time to clinical improvement will be analyze by Kaplan-Meier method and compare with a log-rank test.

Funding sources	In progress
Study will have a Data Safety Monitoring Board	Yes

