12.4 Efficacy Analysis

12.4.1 Main Efficacy Criterion

The primary ITT analysis on the primary endpoint will be carried out by Cox model of survival analysis. Possible interaction between treatment and strata will be tested. The corresponding 95% confidence interval of Hazard ratio will be calculated from Cox model.

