12.7 Randomisation

The randomisation will be stratified by centre and status of cardiac insufficiency (present/absent).

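### The protocol gives two incompatible stratification rules, so the randomisation list and the strata in the interaction test have no single definition

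*Protocol*

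**What the plan says.** The randomisation rule appears three times.

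- Summary, design: "The randomization will be stratified on the indication of RAS blockers", with heart failure against any other indication. Centre is not mentioned.
- Section 4.2.4: "The randomization will be stratified on the indication of RAS blockers (heart failure vs. other indication". Centre is again not mentioned. The same section states "Randomization will be performed with IWRS (Cleanweb" as the system.
- Section 12.7: "The randomisation will be stratified by centre and status of cardiac insufficiency (present/absent".

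Two later statements depend on the strata. Section 12.4.1 says "Possible interaction between treatment and strata will be tested" without naming them. Section 12.8 makes a supplementary power check, "Considering around 25 % of patients in the cardiac insufficiency stratum", for a 5-day difference "in the other stratum that will include n=207 patients/group" (the Summary carries the same sentence). No section reconciles the versions.

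**The concern.** A randomisation list follows one rule. Whoever builds it from 4.2.4 leaves centre out, and whoever builds it from 12.7 puts centre in. The choice cannot be undone for patients already randomised, and section 5.4 plans only one month of enrolment.

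Centre has some relevance here. The primary endpoint counts live discharge as improvement. For a patient who starts in category 3 or 4, a two-point gain leads to category 1 or 2, which are both out of hospital. For these patients the event is therefore discharge, and discharge practice may differ between hospitals. The protocol gives no figures on such variation.

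The heart-failure factor raises a second question. Why a drug was prescribed is not the same as whether a disease is present. A patient with heart failure whose RAS blocker was prescribed for hypertension is in the other-indication stratum under 4.2.4 and in the present stratum under 12.7. The baseline data list in 5.1 names a history of heart failure but does not name the indication of the RAS blocker.

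At stake are a defined allocation procedure, balance within the subgroup that the plan singles out, and an interaction test with one meaning.

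**Working it through.** **Inputs.** N = 554, 277 per arm, 12 centres (4.2.2). About 25% in the cardiac-insufficiency stratum, 207 per group in the other, control median 16 days, difference 5 days, two-sided 0.05, three O'Brien-Fleming looks (12.8).

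**1. The plan's own stratum figure.** (1 - 0.25) x 277 = 207.75, stated as 207. It is reproduced. It uses only the heart-failure share; centre plays no part.

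**2. Allocation cells.**

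| Rule | Factors | Cells | Mean patients per cell |
|---|---|---|---|
| Summary, 4.2.4 | indication (2 levels) | 2 | 554/2 = 277 |
| 12.7 | centre (12) x cardiac insufficiency (2) | 24 | 554/24 = 23.1 |

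At 25%, the cardiac-insufficiency cells would average 0.25 x 554/12 = 11.5 patients per centre.

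**3. Interaction test.** Treatment by the two-level factor has 1 degree of freedom. If centre is also one of the strata, treatment by centre adds 12 - 1 = 11, giving 12.

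**4. Sensitivity of the 207 check to the definition.** The 25% is given for cardiac insufficiency. The share with heart failure as the indication is not stated, so I assume 10% to 40%.

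- The other stratum then has 0.90 x 277 = 249 down to 0.60 x 277 = 166 per group.
- With exponential times the rate ratio is 16/11 = 1.4545. Schoenfeld's formula, events = 4(z_alpha/2 + z_power)^2 / (ln 1.4545)^2, gives 300 events for 90% and 224 for 80%. Inflated for the three looks (factors 1.016 and 1.017), these become 305 and 228.
- An event fraction of 55%, which the protocol does not state, reproduces both power claims: 305/554 = 0.55 and 228/414 = 0.55.
- At that fraction, power in the other stratum runs from 87% (10% share) to 71% (40% share).
- At the exponential 28-day fraction, the mean of 1 - 2^(-28/16) and 1 - 2^(-28/11) = 76.6%, it runs from 95% to 84%.

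This shows how far the check depends on the definition. It does not show that 207 is wrong.

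**5. What is lost if the tested factor was not the randomised one.** As a worst case, take no heart-failure stratification at all. The stratum has 0.25 x 554 = 138.5 patients, about 69 per arm, and the standard deviation of one arm's count is sqrt(138.5)/2 = 5.9. A 2-SD imbalance is a 0.585/0.415 split, which keeps 4 x 0.585 x 0.415 = 97% of the information. In the remaining 415.5 patients the same calculation gives a 0.549/0.451 split and 99%.

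**The case against.** The strongest reply is that this is mostly wording. The Summary stratifies on indication and, in its statistics paragraph, calls the same split the cardiac insufficiency stratum. Both labels therefore seem to stand for one factor, and cardiac insufficiency may simply be a translation of heart failure. This largely stands: indication and status can differ in a patient, but the protocol does not show that two variables were intended.

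It may also be said that the Summary and 4.2.4 never exclude centre, so they could be incomplete beside a fuller 12.7. This does not remove the problem. Section 4.2.4 is the operational section on randomisation, and it names one factor.

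Finally, little statistical harm follows. This stands too: step 5 of the working shows a small loss even in the worst case.

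Three stronger readings are tempting and are not supported:

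- A reader might infer that the trial is sized on a stratum that is not the randomised one. Section 12.8 obtains 277 per group from 90% power overall, and the stratum sentence is an additional check.
- A reader might infer that the primary analysis is stratified on the wrong variable. Sections 12.4.1 and 12.8 name a Cox model and a log-rank test, and neither says that the analysis is stratified.
- A reader might infer that the treatment comparison is biased. Allocation is random 1:1 under either rule.

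**Conclusion.** The contradiction is real and should be fixed. It is firm for centre (2 cells against 24) and probable but less certain for the heart-failure factor. The randomisation list cannot be built from the protocol without someone choosing a rule, and the interaction test has either 1 or 12 degrees of freedom depending on that choice.

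The size of the consequence is modest. The figures 554, 277 and 207 stand, no type I error inflation or bias is shown, and the possible loss is one of balance and precision. How many patients would be classified differently by indication and by status is not given and cannot be derived. The importance of centre rests on an assumption that discharge practice varies between hospitals.

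**What to change.** Before the first patient:

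1. State one set of stratification factors in identical words in the Summary, 4.2.4 and 12.7. Say whether centre is included.
2. Define the heart-failure factor once, for example as the status recorded in the baseline history. Status and indication are both workable if used consistently. I lean to status because 5.1 already collects it, but that is a preference, as is keeping centre.
3. Confirm that the randomisation system is configured to that rule.
4. In 12.4.1, name this heart-failure factor as the one in the interaction test. In 12.8 and the Summary, use the same name for the 25%/207 check and confirm that 25% refers to it.
5. Stratify the log-rank test, and stratify or adjust the Cox model, by that factor.

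The cost is wording in five places and one configuration check. The sample size does not change unless step 4 shows that the 25% belongs to a different definition; in that case only the supplementary 207 check is redone.
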